8.5. Digital Momentary Assessments

The digital momentary assessments are an optional component of the study. A decision not to take part in this component will not preclude involvement in the overall study.

There are three components:

- 1) **Ecological Momentary Assessment (EMA)¹¹⁴** via an existing smartphone app (‘mindLAMP’, available for Android and iOS). EMA will repeatedly measure symptoms and behaviour *in vivo*. The app will prompt participants to complete a short 1-2 minute survey once/day for 12 months assessing daily stress levels, affective states, anomalous experiences and behaviour. Using the same app, short 2 minute audio recordings (an audio diary) will be made on a daily basis. These consist of the participant being prompted to record speech about their recent experiences, events and context.
- 2) **Passive Sensing:** The ‘mindLAMP’ app is capable of automatically (‘passively’) logging context information by via mobile phone sensors. The geolocation (GPS) and accelerometer sensors will be used. The GPS sensor provides a location estimate for the participant’s current location. The accelerometer sensor measures acceleration.
- 3) **Actigraphy:** Participants will wear Axivity AX3 (Newcastle upon Tyne, UK) watches (accelerometers assessing 24h gross motor activity) during the first year to measure rest-activity patterns and physical/sedentary behaviours.

Passive sensing and actigraphy data will be analysed using computer programs and algorithms. Variables extracted for analysis will include: roaming/movement patterns (e.g., distance travelled, maximum distance between two locations), location (e.g., ‘home time’, time spent outdoors), and regularity of movement (e.g., location entropy, diurnal movement index).

8.6. Neurocognitive Tasks

The neurocognitive tasks will be administered via computer, apart from the IQ tests.

The WRAT 5 Reading subtest is a short reading task used to estimate premorbid IQ. This task will only be administered at baseline.

The Wechsler Abbreviated Scale of Intelligence (WASI-II¹⁶²) is a general intelligence, or IQ, test designed to assess specific and overall cognitive capabilities and is individually administered to children, adolescents and adults. Only the Full Scale IQ (FSIQ)-2 section will be completed. We will use the two subtest version to generate a Full Scale IQ. The WASI-II will be administered at baseline and 2 year (104 weeks) follow-up. As the WASI-II is not available in non-English speaking countries, non-English speaking sites will administer the Vocabulary and Matrix Reasoning subtests of the Wechsler Adult Intelligence Scale-V (WAIS-V) for participants aged 16 and above and the Wechsler Intelligence Scale for Children-V (WISC-V) for participants under the age of 16.

A number of tasks from the web-based Penn Computerised Neurocognitive Battery (PennCNB) will be administered at baseline, 8 weeks, 26-weeks, 52-weeks and 104 weeks. They will include measures of attention (Continuous Performance Test), working memory (Letter N-Back), processing speed (Digit-Symbol Substitution Test), relational memory (Digit Symbol Recall), verbal learning (List Learning Test), spatial memory (Visual Object Learning Test), emotion recognition (Emotion Recognition Test), motor function (Finger Tapping Test) and sensorimotor speed (Motor Praxis).

The battery has an estimated administration time of 50 minutes at baseline, 28 minutes at weeks 8, 26 and 52, and 43 minutes at week 104.

8.7. Neurophysiological Assessments (EEG Recordings)

EEG will be acquired during 4 paradigms:

1. **Mismatch Negativity (MMN)/Visual Oddball Paradigm.** The participant performs a visual oddball target detection task while ignoring the auditory tone stimuli presented.
 - a. MMN Paradigm: Measures include
 - i. Mismatch Negativity (MMN) amplitude - Pitch+Duration “Double Deviant tones”.
 - ii. Repetition Positivity (RP) amplitude - difference between late and early appearing standards within a local series of standards in MMN paradigm.
 - b. Visual Oddball Paradigm: Measures include
 - i. Visual Target P300 (P3b) amplitude
 - ii. Visual Novelty P300 (P3a) amplitude
2. **Auditory Oddball Paradigm:** Measures include
 - a. Auditory Target P300 (P3b) amplitude
 - b. Auditory Novelty P300 (P3a) amplitude

- c. Auditory Target and Novel Alpha Desynchronization
3. **40 Hz Auditory Steady State Response:** Measures include
 - a. 40 Hz Inter-trial Phase Coherence (ITC)
 - b. Baseline inter-stimulus interval Gamma Power
4. **Resting state EEG (eyes open/eyes closed):** Measures include
 - a. Power spectra: delta, theta, alpha, beta, gamma
 - b. 1/f slope: Thought to reflect excitation/inhibition balance.

Frequency: EEG data will be acquired at baseline and at 2 month follow up. The protocol for baseline and follow up is identical. The purpose of the follow up assessment is to assess change trajectories predictive of CHR outcomes. Each EEG session will require between 90 minutes and 2 hours from set-up to clean-up.

Instruments: Identical 64-channel ActiChamp High Impedance EEG systems and an air-gapped acquisition computer and stimulus presentation device will be leased from a private vendor (NeuroSig) and installed at all sites.

8.8. Biospecimens

Biomarkers that can be quantified from peripheral tissue (such as plasma, blood cells or hair) are promising indicators of the pathophysiological processes that underlie mental disorders¹¹⁵. As such, peripheral biomarkers may serve multiple purposes, including indicating risk for onset or progression to a more advanced stage, delineating diagnostic entities or informing treatment choice. For this study, we selected biomarkers with an established association with risk and clinical outcomes, relevance to the pathophysiology of mental disorders (psychosis in particular), minimising participant burden, and limiting the invasiveness of specimen collection.

A blood sample (approximately 40ml or 2.5 tablespoons) will be collected to measure: elevations in white blood cells, as current illness may confound numerous biomarkers; biomarkers of immune system, coagulation system, complement system, and oxidative damage (from plasma, serum); DNA for polygenic risk score; and functional assays for redox dysregulation and cell membranes for lipids, e.g., DHA, DPA, AA (from whole blood).

The blood samples will be collected by a qualified phlebotomist at two separate study time points (baseline and month 2). One of the blood tubes (3ml EDTA) will be transferred to a local pathology service for immediate testing. These initial research analytical samples will be destroyed upon analysis according to the standard operating procedures of the respective pathology service. The remaining blood samples will be processed and stored in an -80 Celsius freezer at the Florey Institute of Neuroscience and Mental Health in Melbourne, Australia. PRESCIENT sites outside of Melbourne will store blood samples locally until transporting their bloods to the Florey Institute.

The samples will be shipped from the Florey Institute to a to-be-determined laboratory/ies for analysis. The blood samples and any paperwork accompanying them will be identified by a unique, study-specific code and hence no participant identifying information will be associated with the sample. The code will only be accessible by researchers and relevant study staff involved in the study and the code to link this will be stored securely.

Following the completion of analyses for the study, the remaining blood samples will be shipped to the NIMH Repository and Genomics Resource (NRGR). Samples will be stored in the repository indefinitely and made available to other researchers upon application for future research purposes.

At baseline and month 2, saliva samples will be collected to measure cortisol levels, indicative of stress response. At both baseline and month 2, two vials will be collected at time 1, two vials at time 2 (1 hour later), and two vials at time 3 (two hours from time 1). All saliva samples will be shipped to NRGR. NRGR will then ship 1 vial per time point (i.e., 3 baseline vials and 3 month 2 vials) for each participant to a to be determined commercial lab such as Salimetrics in the US for analysis and store the remaining samples for future research.

Additionally, data from the FIGS (family history of psychiatric disorder) may be used to inform genetic analyses; recorded history of health conditions may inform biomarker analysis; vital signs, current illness and recent physical activity will be captured as they may confound biomarker measurement.

The type of genetic analysis being conducted in this study is not expected to result in information about individual participants' future health, future treatment or risk of having children with a genetic disorder, or information that may be relevant to the health of family members who are not part of the project.

8.9. Speech and facial expression samples

For the central assessment, audio and video will be recorded using a web-based meeting platform (Zoom). This will consist of an open-ended conversation (approximately 20 minutes in length) to elicit free natural speech, following methods applied previously by our group. RAs use qualitative interviewing methods to elicit description of subjective experience. RAs will be trained to minimize interruption, and use clarifying questions to promote speech production. Open-ended questions were chosen for their ability to encourage introspection and longer speech samples, enabling the analysis of speech coherence and spontaneous content. Moreover, open-ended questions may help to reduce attrition by encouraging rapport building between the administrator and the participant. Two additional speech assessments

will be performed: audio recordings of the PSYCHS semi-structured interviews and daily audio diaries collected during ecological momentary assessment (EMA).

The audio recordings will be used to collect speech content/structure (semantics and syntax) and speech acoustics. For the open-ended interviews, video recordings will be used to collect facial expressions. Audio files from the open-ended and PSYCHS interviews will be sent to a transcription service (TranscribeMe) to obtain pseudo-anonymised transcripts that have been diarized and timestamped for further analysis. The software package OpenSmile will be used to extract information about speech acoustics from the open-ended interviews, the PSYCHS interviews, and the audio diary. The software package OpenFace will be used to extract information about facial expressions from the open-ended interview. Transcription of the audio diaries from EMA (see 8.5) will be processed by automated transcription.

8.10. Neuroimaging

The MRI protocol will collect 4 measurements:

1. **T1** (7 min) - A Magnetization Prepared Rapid Acquisition Gradient Echo (MPRAGE) with high spatial resolution (1mm or better) that provides an excellent contrast between gray and white matter. This measure is required for anatomical segmentation of the brain.
2. **T2** (6 min) - A fast spin echo acquisition with flip angle evolution (SPACE) acquired at the same spatial resolution as the T1. This measure is required to provide complementary anatomical information to the T1.
3. **Diffusion MRI** (11 min) - A multi-shell multi-band spin echo acquisition sensitive to water molecule displacement. This provides microstructural information (most robustly in white matter) as well as macroscopic structural brain connectivity measures. Multi-shell enables sensitivity to different displacement scales, enabling more complex biological models. Multi-band allows simultaneous acquisition of slices at different brain locations, shortening the length of the acquisition.
4. **Resting-state functional MRI** (21 min) - A multi-band gradient echo acquisition sensitive to blood oxygen levels (BOLD) most robustly in gray matter. This measure provides an estimate of functional connectivity within and between particular brain networks.

The protocol for baseline and follow up is identical. The follow up scan will be useful for incorporating into prediction models based on changes over time.

Instruments: All 3T magnets. Due to the variety of MRI systems across the different sites two tiers will be used:

1. **High end tier** (tier 1) - will use Siemens Prisma machines that are currently available or to be installed at most sites across PRESCIENT and ProNET. All Prisma sites will use identical protocols.
2. **Lower end tier** (tier 2) - for all other scanners across PRESCIENT and ProNET. These scanners include Siemens Skyra (3 sites), GE MR750 (4 sites), Siemens Vida

(2 sites), and Philips Achieva DDAS (1 site). The main differences between tier 1 and tier 2 will be in the diffusion scan, where tier 2 will not have the highest shell of diffusion weighting and may use lower spatial resolution. Due to the high instrument variability, the tier 2 protocol will not be identical across sites, although it will minimize differences as much as possible.

PRESCIENT will recruit up to 5 healthy volunteers per site to test the collection and data transfer procedures for the MRI. These pilot/technical scans will be conducted for each machine prior to the commencement of the participant research scans. A total of 250 demographically matched healthy controls; all sites also have considerable experience recruiting adolescent and young adult typically developing control subjects.

8.11. Treatment received

At each follow up assessment, treatment received since last assessment will be recorded. This will consist of both pharmacological and psychosocial treatment and service use. This information will be extracted from the participant interview and, as required, medical files, family and/or pharmacist. Participants who are started on an antipsychotic medication over the course of the study, regardless of whether they meet conversion to psychosis criteria, will be followed up as per the schedule of assessments.

8.12. Engagement Phone Calls and Text Messages

Study participants will be contacted in between the formal assessments for the purposes of engagement and safety follow-up. Potential safety data will be recorded, including any reported adverse events (AE) and serious adverse events (SAEs), and escalated in accordance with safety reporting procedures. These phone calls and texts will be used as a tool to increase engagement and potentially decrease participant attrition, as in other CHR studies being led by the research team. Participants can nominate which mode of contact they would prefer (e.g. phone call, text message etc.). As with all studies, participation is voluntary and all contact attempts will be ceased upon request.

8.13. Data from other sources

If CHR participants are unable to be re-interviewed for the follow up assessments, their diagnostic status at last clinical contact will be sourced from alternative sources, such as medical record files and state medical records (e.g., the CMI database for Victoria, Australia).

9. Safety Measures

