5.5. Study Endpoints and Outcome Measures

Participants will be followed up at regular intervals over a 24-month period (see assessment schedule in 8.1). The primary outcome timepoint of interest is the 24-month follow point. Outcomes of interest are listed below:

Conversion to psychotic disorder. This is operationalised, as:

(A) At least one full threshold positive psychotic symptom as operationalised using the PSYCHS for one week or longer occurring (i) for more than an hour a day, 3-6 days per week OR (ii) daily for less than one hour

OR

(B) At least one full threshold positive psychotic symptom with the above frequency but lasting less than one week in the context of newly prescribed or newly increased antipsychotic medication

OR

(C) At least one full threshold positive psychotic symptom that is immediately dangerous – as assessed by the treating psychiatrist.

The projected number of converted cases across AMP SCZ is 300 (15% conversion rate)⁷.

*Remission of CHR status*⁷. The definition of remission from CHR status has previously been published⁸⁷ and is currently being used in our ongoing intervention trial²⁸. It is modelled on the schizophrenia course definitions presented by the Remission in Schizophrenia Working Group (RSWG)⁸⁸ and was agreed upon using a consensus process amongst CHR clinical and research experts. It requires no longer having attenuated psychotic symptoms in the CHR range, as assessed using the PSYCHS. For the Trait and State Risk Factor and Brief Limited Intermittent Psychotic Symptoms (BLIPS) groups, remission is defined as having achieved good functioning and no longer meeting criteria for schizotypal personality disorder (if present at baseline) and not having had onset of attenuated psychotic symptoms in the CHR range.

*Recovery from CHR status*⁷. Remission maintained for at least six months.

*Relapse of CHR status*⁷. Presence of CHR status after recovery (i.e., meeting PSYCHS severity, frequency and duration criteria for CHR status after recovery has been achieved).

Persistent non-psychotic disorders. A non-psychotic disorder which is present both at study entry and at outcome time point and from which full remission has not been achieved over

the interim. This will be determined using the Structured Clinical Interview for DSM-5 (SCID-5).

Incident non-psychotic disorders. A non-psychotic disorder present over the follow up period but not present at study entry. This will be determined using the SCID-5.

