5.5.1. Primary outcome

The primary outcome of interest is conversion to psychotic disorder by 24 month follow up (definition in 5.4).

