Participants from both samples will be assessed at Baseline. Refer to Section 8.0 for a full list of the measures and their explanation. The CHR sample will be followed up at regular intervals (see 8.0) for a total period of two years. A two year follow up period has been found to capture most CHR cases who convert to psychotic disorder⁹¹. Contact will be made with CHR participants between assessment time points (via phone calls, text messages or emails) in order to maintain engagement and address any technological troubleshooting issues with the digital momentary assessments. It is intended that if CHR participants are unable to be re-interviewed, their diagnostic status at last clinical contact will be sourced from their medical record files and state medical records (the client management interface [CMI] database for Victoria, Australia or local equivalent). HC participants will be assessed at baseline, at 2-month follow up, and at 12-month and 24-month follow up (see section 8.0).

The **screening visit** will take approximately 2 hours to complete. The **full baseline assessments** will take approximately 9–10 hours to complete (3-4 hours for clinical assessments, 1 hour for neurocognitive assessment, 2 hours for neurophysiological

assessments, 1.5 hours for neuroimaging, 20 minutes for free speech recording, and 30 minutes for blood). A saliva sample will be also be collected during one of the baseline visits. The baseline assessments may be completed over multiple sessions in order to minimise participant fatigue. There will also be a 30-min induction/information session at baseline for the digital momentary assessment component. The approximate duration of **follow up assessments** are as follows:

- **Months 1 and 3:** (90 minutes for clinical assessment)
- **Months 2:** 7.5 -8.5 (2-3 hours for clinical assessment, 45 minutes for neurocognitive assessment, 2 hours for neurophysiological assessment, 20 minutes for free speech recording, 30 minutes for blood, and 1.5 hours for neuroimaging)
- **Months 4, 5, 7, 8, 9, 10 and 11:** 20 minutes (BPRS clinical assessment only)
- **Month 6:** 2.5 hours (2 hours for clinical assessment and 30 minutes for neurocognitive assessment)
- **Month 12:** 3.5-4 hours (2.5-3 hours for clinical assessment, and 30 minutes for neurocognitive assessment)
- **Month 18:** 2 hours (clinical assessment)
- **Month 24:** 3.5 hours (2.5-3 hours for clinical assessment and 45 minutes for neurocognitive assessment)

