7.2. Sample Size and Power

The size of the CHR sample is primarily determined by the aim of developing a prediction model for conversion to psychosis by 24 months (the primary outcome of interest). This will be achieved by combining data from the PRESCIENT and ProNET networks (i.e., the AMP SCZ dataset as whole), given that the protocols and schedule of assessments have been harmonised across the two networks. The projected CHR sample size for PRESCIENT is 937 and for ProNET 1,040 (combined n of 1,977). There is no uniform method for determining an adequate sample size for developing a prediction model⁹². In this sample size calculation, the method recently described by Riley et al⁹³ was used. Minimum sample size calculations required for various scenarios are provided in table 1. below. Specifically, the sample sizes were derived for the scenarios of having low, medium or high prediction performance and also for the number of parameters in the model being 10, 20, 30, 40 or 50. Conversion to psychosis is a time-to-event outcome and therefore a survival model such as Cox regression is appropriate. The table below shows the sample sizes for the survival outcome, assuming a conversion rate of 15% over 2 years (number of events=300).

Table 1. Minimum sample sizes for survival outcome.

		Number of parameters in model				
		10	20	30	40	50
Predictive performance	low	422	843	1265	1686	2108
	medium	398	796	1193	1591	1989
	high	366	732	1098	1464	1830

It is undesirable to have the number of parameters above 30 as this would result in a prediction model that is overly cumbersome in real-world settings. As indicated in the table, the minimum sample size for a model with 30 parameters is estimated to be between 1100 and 1300. However, as in all medical research, larger sample sizes lead to more robust models and it would therefore be desirable to achieve a sample size larger than this minimum recommendation. Therefore, we aim to assemble as large a sample as possible given the constraints of the length of the recruitment period and the number of recruitment sites. The sample size calculations presented in the table indicate that the overall AMP SCZ sample size of 1,977 is adequate for developing a prediction model with ~30 parameters that has high predictive performance, while still allowing a subset of the data to be 'held back' for external validation purposes (see section 14).

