8.3. Clinical Assessments

Informed by the recent advances in the field (see section 5.2), the study aims to collect multimodal data (clinical, biological, genetic, neurocognitive, neurophysiological, neuroimaging), baseline and repeat assessments over time ('macro' level monthly assessments) and 'micro-level' momentary (day-to-day) data collected through digital platforms (EMA and passive sensing). The 'macro' level repeat assessments are critical for both dynamic prediction of outcomes and also accurate characterization of clinical trajectories over time.

The battery of assessments are listed in 8.1 and described below. The selection of measures is informed by the Neurobiology in Youth Mental Health Partnership¹⁰¹, a national effort led by Orygen to standardize research assessments in order to create large datasets, guided by principles of feasibility, participant and clinical service burden, transdiagnostic relevance and translatability into clinical practice.

The following measures will be administered by RAs as part of an integrated clinical interview:

The **Positive Symptoms and Diagnostic Criteria for the CAARMS Harmonized with the SIPS (PSYCHS)** is a semi-structured interview which assesses symptoms associated with the prodromal phase of psychosis, and which is used to define the CHR criteria and onset of first-episode psychosis (FEP). The attenuated psychotic symptoms (positive symptoms) section of the PSYCHS will be assessed at all major assessment timepoints. This will be a rating of the worst period of each symptom either (1) over the last year (at Screener) or (2) since the participant's last research assessment.

The **Structured Clinical Interview for DSM-5 (SCID-5)** is a semi structured interview guide for determining DSM-5 diagnoses. The SCID-5-Research Version (RV)⁹⁷ will be used to assess DSM diagnostic criteria for Mood and Substance Use disorders and the SCID-5 Personality Disorders (PD)¹⁰² will be used to assess Schizotypal Personality disorder. If the participant converts to psychotic disorder, as determined using the PSYCHS, then the Psychotic Disorder section of the SCID-5-RV will be administered to determine type of DSM psychotic disorder. The language and diagnostic coverage

make the SCID-5 most appropriate for use with adults (age 18 and over); with slight modification to the wording of questions it may be used with adolescents.

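### For participants lost to interview, 6.4 and 8.13 collect a point diagnosis without an onset date, although the primary outcome is a first conversion at any time up to 24 months

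*Protocol*

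**What the plan says.** Section 5.5.1 sets the endpoint: "The primary outcome of interest is conversion to psychotic disorder by 24 month follow up". It points to 5.4 for the definition, which stands in 5.5. Criterion A there reads "At least one full threshold positive psychotic symptom as operationalised using the PSYCHS for one week or longer", followed by a frequency rule. Criterion B admits an episode "lasting less than one week in the context of newly prescribed or newly increased antipsychotic medication", and criterion C covers a full-threshold symptom judged immediately dangerous. Section 7.2 fixes the type of analysis: "Conversion to psychosis is a time-to-event outcome and therefore a survival model such as Cox regression is appropriate".

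At follow-up interviews, section 8.3 has the PSYCHS rate the worst period of each symptom "since the participant's last research assessment", so each interview looks back over the whole interval.

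For CHR participants who cannot be re-interviewed, section 6.4 states an intention that "their diagnostic status at last clinical contact will be sourced from their medical record files and state medical records", naming the Victorian database or a local equivalent. Section 8.13 repeats it: "their diagnostic status at last clinical contact will be sourced from alternative sources, such as medical record files and state medical records". Section 7.10 adds attempts to re-contact the participant and use of the record system to see whether the person has been in touch with other mental health services. None of these sections asks for an earlier episode, an onset date or a comparison of the record with criteria A to C.

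**The concern.** The interview route and the record route measure different things. The interview asks whether the threshold was crossed at any time since the last assessment. The record route asks what diagnosis the person carries when last seen by a service. A conversion under 5.5 need last only a week, or less under criterion B, so it can be over by the last contact and leave a non-psychotic diagnosis there. Where the record does show psychosis, the date of last contact is not the date of onset, and a Cox or joint model needs the latter. A clinical diagnosis can also err the other way and count someone who would not meet A to C.

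This matters at protocol level because it governs what is collected. An analysis plan can decide how to code or censor, but it cannot recover an earlier episode or an onset date that nobody extracted.

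**Working it through.** **The two routes side by side**

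| | Interview (5.5, 8.3) | Records (6.4, 8.13) |
|---|---|---|
| Period covered | whole interval since last research assessment | one moment, the last contact |
| Test applied | PSYCHS criteria A to C | clinical diagnosis |
| Onset date | obtainable for the interval | not requested |

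Section 8.3 also keeps conversion and diagnosis apart: the PSYCHS determines conversion, and only then does the SCID-5 psychotic section determine the type of disorder. The record route collects something like the second without the first.

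**Who is exposed**

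1. Anyone interviewed again later is covered, because the PSYCHS reaches back to the last research assessment.
2. Up to month 12 the BPRS is monthly, and a suspected conversion triggers the PSYCHS and SCID (8.1, note 5). This helps only while the participant attends.
3. After month 12 the scheduled PSYCHS visits are months 18 and 24 (8.1).
4. The exposed group is therefore those never interviewed again, and only for the time after their last completed assessment.

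**The plan's own event figure**

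Section 7.2 works from "assuming a conversion rate of 15% over 2 years (number of events=300" in the combined sample. 937 + 1,040 = 1,977, and 0.15 × 1,977 = 296.55, which agrees with the rounded 300. This protocol governs PRESCIENT only: 0.15 × 937 = 140.55, about 141 conversions.

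**Illustration of size, on assumed inputs**

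Missed conversions = 140.55 × f × g × m, where
- f = share of converters permanently lost to interview. Not in the protocol; assumed 0.10 to 0.40.
- g = share of those people's conversions that fall after their last completed assessment. Not in the protocol; at most 1, with 0.5 shown for comparison.
- m = share of those conversions no longer visible as psychosis at the last contact. Not in the protocol; assumed 0.10 to 0.50.

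| f | m | g = 1 (ceiling) | g = 0.5 |
|---|---|---|---|
| 0.10 | 0.10 | 140.55 × 0.010 = 1.4 | 0.7 |
| 0.20 | 0.25 | 140.55 × 0.050 = 7.0 | 3.5 |
| 0.40 | 0.50 | 140.55 × 0.200 = 28.1 | 14.1 |

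The ceiling is 1% to 20% of the 141. Setting g = 1 overstates the loss unless everyone in the group leaves straight after baseline, since conversions before loss are already captured by the PSYCHS. The count covers missed events only. Events that are found but lack an onset date, and chart diagnoses that would fail A to C, come on top and cannot be sized from the document.

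**The case against.** The strongest reply is that the protocol never says the sourced status becomes the primary outcome. It says only that the status will be obtained, and diagnostic status also serves the secondary outcomes on non-psychotic disorders. This stands as a limit on how firmly the point can be put. But the record status takes the place of the missing interview, section 6.4 introduces it shortly after arguing that two years captures most converters, and no other route to the endpoint is given for these people.

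A reader might infer more, and the document does not support it:
- **Someone last seen at month 4 is counted as non-converted at 24 months.** No section says so. The planned time-to-event models would ordinarily censor such a person, and the censoring rule may properly sit in the analysis plan.
- **A diagnosis made after month 24 would count.** The synopsis (section 4, Study Endpoints) limits clinical data to the 24-month time point, and 5.5.1 bounds the outcome there.
- **A resolved month-8 episode is lost whenever a visit is missed.** It is lost only if no later interview takes place. Monthly BPRS, the triggered assessments, the re-contact efforts in 7.10 and the engagement calls in 8.12 all reduce that risk.
- **Site differences in records will show up as poor calibration.** Record systems do differ by country, but the document gives nothing to show how much, so this is only a possibility.

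It is also fair to say that charts may not hold the hours-per-day and days-per-week detail that criterion A requires. That limits how completely the criteria can be applied. It does not justify asking for less than the record contains.

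**Conclusion.** The point holds in a limited form. For participants permanently lost to interview, 6.4 and 8.13 ask for a point status that does not match a dated first-event outcome. Followed as written, a conversion after the last completed assessment that has resolved by the last contact goes unrecorded, any conversion found has no event time, and a chart diagnosis is not referred to criteria A to C. The size cannot be derived, because the protocol gives neither a loss rate nor the proportion of conversions that remain visible in records. The 1 to 28 of about 141 shown above is a ceiling on assumed inputs, not an estimate. The conclusion rests on one inference, that the sourced status is meant to stand in for the missing outcome interview. It is worth correcting because the information cannot be recovered later and the change is small.

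**What to change.** In 6.4 and 8.13, replace the point status with a review of all available record contacts from the last completed PSYCHS to month 24, looking for any first psychotic episode. For each participant, record:

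- whether such an episode is documented, and its earliest documented date;
- a rating against criteria A to C as far as the record allows, with an explicit category for insufficient detail;
- a flag that the outcome is record-derived;
- the date of the last informative contact, so that those without an episode can be censored there.

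The censoring rule itself, and any repeat analysis restricted to interview-confirmed events, can be left to the analysis plan once these items are collected.

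The cost is a wording change in two sections, an extraction form and some added time per lost participant, on records the protocol already intends to open. The remaining weakness is that some records will not hold the frequency and duration detail needed to apply A to C fully. The flag and the insufficient-detail category make that visible.
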